2.2.4 Supportive Secondary Endpoints

Consumption of N8-GP (number of infusions and U/Kg) per bleed

The number of infusions per bleed will be summarised and listed.

The number of U/Kg per bleed will be summarised and listed.

Consumption of N8-GP (number of infusions and U/Kg per month and per year) during prophylaxis and on-demand treatment

The number of infusions per month and per year will be summarised and listed by treatment regimen (prophylaxis and on-demand).

The number of U/Kg per month and per year will be summarised and listed by treatment regimen (prophylaxis and on-demand).

Haemostatic effect as measured by recovery and trough levels FVIII:C (in all patients in the prophylaxis treatment arm)

Recovery and trough levels measured at scheduled visits will be summarised and listed.

2.2.4.1 PK Endpoints

- FVIII activity 30 min post-injection ($C_{30\text{min}}$)
- Incremental recovery, ($[\text{IU/mL}] / [\text{U/kg}]$) (single dose and steady state)
- Trough level, (IU/mL) (single dose and steady state)
- Area under the curve (AUC), ($\text{h} \cdot \text{IU/mL}$)

- Terminal half-life ($t_{1/2}$), (h)
- Clearance (mL/h/kg)
- Mean Residence time (MRT) (h)
- Volume of distribution at steady state (V_{ss}) (mL)
- Apparent volume of distribution (V_z) (mL)
- Percentage of $AUC_{(0-inf)}$ determined by extrapolation (%extrap)
- Terminal elimination rate constant (λ_z)

Single dose PK will be based on the subgroup of patients with full PK sessions at Visits 2 and 7. Steady state PK will be based on the periodic recovery and pre-dose measurements on all patients from Visits 3 to 13:

Single dose PK

The PK parameters will be calculated using plasma concentration obtained from chromogenic assay and clot assay. The PK parameters will be derived according to a non-compartmental method, as described in [Table 2-2](#). The actual time points will be used in the calculations.

If any profiles and/or individual plasma concentrations are excluded from the primary pharmacokinetic analysis, a sensitivity pharmacokinetic analysis will also be performed and reported based on all observed data. The primary pharmacokinetic analysis is based on the full analysis set excluding outliers.

Specifically which data points and profiles that will be excluded will be defined prior to database lock. It should exclude profiles with pre-dosing activity > 5% (possibly indicating inadequate washout) and profiles that are not indicative of a normal intravenously short infusion administration (e.g. clearly increasing plasma concentrations initially). If a patient is treated with an additional dose during the PK session, the plasma concentrations after the occurrence will then be excluded. Furthermore, if the profile shows indications of an additional dose (e.g. clearly increased plasma concentration), the plasma concentrations after the occurrence will then also be excluded.

All pharmacokinetic endpoints (except MRT, V_{ss} , V_z , percentage of $AUC_{(0-inf)}$ determined by extrapolation and Terminal elimination rate constant) will be analysed using mixed effects model on log-transformed parameters including visit as fixed effect, and patient as random effects. Estimates of each endpoint with 95% confidence intervals will be provided back-transformed to the natural scale. In addition, AUC and C_{30min} will be compared between the 2 visits as estimated ratio between the two visits together with the 90% confidence intervals.

All PK profiles will be presented graphically by subject and by visit.

Furthermore, the mean PK endpoints will be summarised and individual PK endpoints will be listed.

Table 2–2 Definition and Calculation of PK Parameters

Parameter	Description	Calculation
Incremental Recovery	Dose-normalised activity recorded 30 min after end of infusion and reported as [IU/mL]/[U/kg]. Expected to be the highest dose-normalised activity observed.	The incremental recovery is calculated by subtracting the FVIII activity (IU/mL) measured in plasma at time 0 from that measured at time 30 min after dosing and dividing this difference by the dose injected at time 0 expressed as U/kg BW
C _{30min}	The FVIII activity recorded 30 min after end of infusion. Measure of maximum exposure	The FVIII activity recorded 30 min after end of infusion. The value is sensitive to deviations from the scheduled sampling time. This limits the value of this parameter, especially when comparing to other studies.
Trough level	Activity recorded immediately before next dose is given and reported as [IU/mL]. Expected to be the lowest dose-normalised activity observed.	
t _{1/2}	Terminal half-life	$t_{1/2} = \ln(2) / \lambda_z$, where λ_z is the terminal elimination rate. The terminal elimination rate will be estimated using linear regression on the terminal part of the log(activity) versus time profile
CL	Total plasma clearance of drug after intravenous administration	CL= Dose / AUC
AUC _(0-inf)	Area under the activity versus time profile from time zero to infinity. Measure of total plasma exposure.	$AUC = AUC_{(0-t)} + C_{(t)} / \lambda_z$, where $C_{(t)}$ is the last measurable activity.
AUC _(0-t)	Area under the plasma activity versus time profile from time zero to the last measurable activity. Measure of plasma exposure in the time interval 0 to last measurable activity.	AUC(0-t) is calculated using the linear trapezoidal method from time 0 to the time for the last measurable activity. The activity at time 0 will be estimated by log-linear back extrapolation of the two initial post-administration activities. If the second value is not lower than the first value, the concentration at time 0 will be defined as

		the highest of these two.
V_z	Apparent volume of distribution based on the terminal phase	$V_z = CL/\lambda_z$
V_{ss}	Apparent volume of distribution at steady-state	$V_{ss} = CL \times MRT$
%extrap	Percentage of AUC(0-inf) determined by extrapolation	$AUC_{t-inf}/(AUC(0-inf))$
MRT	Mean Residence Time	$MRT = AUMC/AUC(0-inf)$, where AUMC is the area under the first moment curve, i.e. the area under the curve $t \cdot C(t)$, calculated with the same method as AUC(0-inf) (linear trapezoidal method + extrapolated area)
λ_z	Terminal elimination rate constant	The terminal elimination rate constant will be estimated using linear regression on the terminal part of the log(activity) versus time profile

Since no new single dose PK profiles have been collected since main phase, PK parameters will not be reported for the extension phase part 2 interim.

Steady state PK

The following rules will be implemented for pre-dose activity, post dose activity and incremental recovery:

- FVIII activity data will be excluded if post-dose activity is \leq pre-dose FVIII activity.
- Samples drawn more than ± 2 days from planned time as well as less than twice the prophylaxis treatment interval after last treatment of bleed will be excluded.
- For patients performing a PK session at Visit 7 (including a wash-out period), the pre- and post-dose data will be excluded from calculation of mean trough and mean recovery. The incremental recovery will still be calculated.
- Samples for randomised patients in extension phase part 1 changing from every 7 day dosing to every 4 day dosing will be excluded from change of treatment regimen and onwards.
- Samples taken at “return visit” from the surgery trial (NN7088-3860)

- FVIII activity measured in defrosted plasma samples will be excluded.

The pre-dose FVIII activity levels assessed from after at least 4 PPX dosing intervals will be analysed to get an estimate of the pre-dose level for N8-GP at steady state. The model will be a mixed model on the logarithmic plasma activity levels with dose and age as a factor and patient as a random effect. Plasma concentrations below lower limit of quantification (LLOQ) will be set to half the value of the LLOQ. The estimated pre-dose FVIII level will be presented together with the 95% confidence intervals. Trial duration for the main phase differs between patients, but all patients reach at least Visit 8 prior to being transferred to Visit 13 (end of main phase). Therefore, the analysis will be performed both on pre-dose values from main and extension phase part 1 and furthermore including only pre-dose values up to visit 8.

A sensitivity analysis including all data after at least 4 PPX dosing intervals will also be performed for both cases.

Furthermore the same analyses will be performed for measurements from the randomised patients in the extension phase part 1.

Pre-dose activity, post-dose activity and incremental recovery will be summarised by visit. Furthermore, mean pre-dose activity and mean post-dose activity will be plotted vs. time.

In extension phase part 2, the only PK endpoint that will be summarised by visit is incremental recovery for all prophylaxis patients, since incremental recovery is independent of dose and dosing frequency. Incremental recovery will be calculated using the same activity measurements as used for estimation of recovery and trough levels.

In extension phase part 2 the following rules have been added to the rules for activity measurements listed above (the new rules are also applied to activity measurements from main and extension phase part 1)

- Samples from visits when changing treatment regimen (e.g. from every 4 day dosing to every 7 day dosing) will be excluded (this rule replaces the rule for randomised patients changing from every 7 day dosing to every 4 day dosing)
- Samples taken at “return visit” from the PK-trial (NN7088-4033) are excluded.
- If the FVIII activity is above 3.0 IU/ml based on one of the three clot assays and the ratio of Clot PSS (chrom)/Chrom PSS > 1.5, all clot data for this sample time point will be excluded. The reason for this rule is that plasma samples can be activated during pre-

analytical handling resulting in very high FVIII activity measured with one-stage clot assay but not with the chromogenic assay.

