3.1 Basic Information

3.1.1 Haemophilia A

Haemophilia A is a recessive X-linked congenital bleeding disorder caused by mutations in the coagulation factor VIII gene on the long arm of the X-chromosome. According to the World Federation of Haemophilia (WFH), there are globally 320,000 – 340,000 patients with haemophilia A of which only approximately one quarter receives adequate care¹.

With a deficiency or absence of FVIII, activation of coagulation factor X becomes severely impaired, and consequently, the thrombin burst becomes delayed and insufficient for normal haemostasis². The haemostatic plug formed in these patients is, if formed, fragile and easily dissolved by normal fibrinolytic activity, leading to impaired haemostasis, prolonged bleeding episodes and re-bleeding. The bleeding episodes in patients with severe haemophilia A are typically spontaneous or after mild trauma in joints, muscles and soft tissues. The bleeding episodes often occur in the muscles and joints of the elbows, knees and ankles, causing acute haemarthrosis. In repeated cases this is followed by synovitis in the affected joint. Recurrent bleeding episodes in the same location, may lead to chronic arthropathy, muscular atrophy and deformities³. Bleeding episodes may occur in all parts of the body including life-threatening bleeding episodes in the central nervous system (CNS), throat, neck, gastrointestinal tract, retroperitoneum or external injuries. As the Human Immunodeficiency Virus (HIV) and Hepatitis C (HCV) epidemics have subsided, the most serious complication to haemophilia treatment is inhibitor development. Inhibitors are allogeneic antibodies to FVIII that reduce or eliminate the activity of FVIII proteins in clotting factor concentrates. This condition develops in as many as 30–35% of previously untreated patients (PUPs) with severe haemophilia A^{4,5}. Hence, the risk of inhibitor development related to the individual product should be initially evaluated in PTPs as these patients have been exposed to previous FVIII products and considered to be at a low risk of developing inhibitors and therefore the most suitable for trial population.

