5.1 Type of Trial

This phase 3 trial is a multi-centre, multi-national, open-label, non-randomised trial evaluating safety, pharmacokinetics and clinical efficacy of N8-GP when used for treatment of bleeding episodes and for long-term prophylaxis.

A minimum of 115 patients must complete the trial including at least 10 patients in on-demand treatment and 105 patients in prophylaxis treatment with N8-GP every 4 days. In order to ensure recruitment of patients for PK it is planned that the first patients (approximately 10) entering the prophylaxis arm must undergo PK sessions. Whether a patient will receive prophylaxis treatment or on-demand treatment is non randomised and will be the choice of the patient and Investigator. This will be based on medical needs and decided at the Screening visit. For the US, recruitment will open for the on-demand arm before enrolling patients in the prophylaxis arm, whereas both arms will open concurrently at non-US sites. The distribution of patients will be as follows:

- It is expected that approximately 120 patients will be dosed in the prophylaxis arm in order to obtain 105 completed patients on prophylaxis treatment. These patients will receive treatment with 50 U/kg of N8-GP every 4 days during a period of approximately 7-19 months. In case of a bleed the patients will be treated with doses between 20-75 U/kg BW.
- It is expected that approximately 12 patients will be enrolled in the on-demand arm to obtain 10 completed patients who have been treated on-demand with N8-GP during a period of approximately 6 months. In case of a bleed the patients will be treated with doses between 20-75 U/kg BW. When they have completed approximately 6 months on-demand treatment, the on-demand patients will be offered to switch to the prophylaxis arm if, the prophylaxis arm is still open for enrollment, or to continue on-demand treatment until the end of trial.

A minimum of 15 of the patients in the prophylaxis arm must undergo 2 PK sessions to obtain 13 patients with two usable PK profiles each. The first PK session will take place at Visit 2a and the second will take place at Visit 7. When 15 patients have successfully completed the two PK sessions and data is available, no additional patients will be required to undergo PK assessments. Furthermore, recovery and trough levels of FVIII will be followed throughout the trial at all visits for all patients on prophylaxis to evaluate steady-state and indications of inhibitor formation.

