18.2.4 Supportive Secondary Endpoints

Consumption of N8-GP (number of infusions and U/Kg) per bleed

The Number of Infusions per bleed will be summarised and listed.

The number of U/Kg per bleed will be summarised and listed.

Consumption of N8-GP (number of infusions and U/Kg per month and per year) during prophylaxis and on-demand treatment

The number of infusions per month and per year will be summarised and listed by treatment regimen (prophylaxis and on-demand)

The number of U/Kg per month and per year will be summarised and listed by treatment regimen (prophylaxis and on-demand)

Haemostatic effect as measured by recovery and trough levels FVIII:C (in all patients in the prophylaxis treatment arm)

Recovery and trough levels measured at scheduled visits will be summarised and listed.

A sensitivity analysis will be performed excluding troughs > 30% and excluding recoveries < 30%. This will aim to eliminate any troughs recorded as recoveries and vice versa that has not been possible to clarify during data cleaning.

~~18. 2.4.1 The Number of Injections of N8-GP required per Bleed~~

~~This endpoint will be summarised and listed.~~

~~— Amount of N8-GP required per Bleed~~

~~Amount of N8-GP required per bleed (U/kg BW/bleeding episode) will be summarised and listed~~

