Only treatment requiring bleeding episodes will be considered in the above evaluations of ABR. Incidence rate of FVIII-inhibitor and haemostatic effect of N8-GP when used for treatment of bleeding episodes will be evaluated based on accumulated data (Main Phase + Extension Phase part 1).

Adverse events, consumption of N8-GP, recovery and pre-dose levels will be summarised based on accumulated data (Main + Extension Phase part 1) by treatment regimen combining the every 4 day dosing regimens. In addition, separate summaries including data from part 1 only will be presented by treatment regimen for the randomised subset of patients to support the main objective of part 1 of the Extension Phase.

Other safety endpoints will be summarised based on accumulated data (Main Phase + Extension Phase part 1). Binding non-inhibitory antibodies will be listed.

PRO endpoints at end the Extension Phase part 1 will be evaluated and presented as described in section 18.9.

Data from part 2 of the Extension Phase

The main objective of extension phase part 2 is to collect long term safety and efficacy data.

ABR will be calculated as for the co-primary endpoint in the main phase, but based on the accumulated data, i.e. combined data from main phase, extension phase part 1 and extension phase part 2. Furthermore, sensitivity analyses are performed based on actual bleeding episodes and exposure times (i.e. without imputation for withdrawn patients).

Incidence rate of FVIII-inhibitor and haemostatic effect of N8-GP when used for treatment of bleeding episodes will be evaluated based on accumulated data.

Adverse events and consumption of N8-GP will be summarised based on accumulated data by treatment regimen.

Incremental recovery will be summarised by visit for extension phase part 2 and furthermore be presented graphically in the following ways:

- By N8-GP production process (extension phase part 2 data)
- According to Anti-PEG-antibody status (accumulated data)

For Anti-CHO HCP-antibodies, the number of negative/positive samples will be summarised by visit.

Other safety endpoints will be listed and/or plotted based on accumulated data.

-

PRO endpoints for extension phase part 2 will be summarised by time since first dose (since timing of visits depend on treatment regimen). Time grouping will span a year, i.e. grouping being “1 - <2 years”, “2 - <3 years”,.... The two prophylaxis regimens will be considered as a combined prophylaxis treatment regimen.

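### The steady-state PK rule that drops data when post-dose activity does not exceed pre-dose removes every incremental recovery of zero or below, without evidence of a sampling error and with no all-data recovery analysis planned

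*SAP*

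**What the plan says.** SAP 2.2.4.1 introduces its steady-state exclusions with "The following rules will be implemented for pre-dose activity, post dose activity and incremental recovery". The first rule reads "FVIII activity data will be excluded if post-dose activity is" less than or equal to the pre-dose activity. No further condition or exception is attached.

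Table 2-2 in the same section obtains incremental recovery "by subtracting the FVIII activity (IU/mL) measured in plasma at time 0 from that measured at time 30 min after dosing" and divides the difference by the dose in U/kg. For extension part 2, where incremental recovery is the only PK endpoint summarised by visit, "Incremental recovery will be calculated using the same activity measurements as used for estimation of recovery and trough levels". SAP 2.10 then presents recovery graphically, including "According to Anti-PEG-antibody status (accumulated data"), and SAP 2.4 names the same plots as the anti-PEG output.

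The protocol gives recovery a surveillance role. Section 5.1 has recovery and trough levels followed throughout for all "patients on prophylaxis to evaluate steady-state and indications of inhibitor formation". Section 3.1.1 says: "Inhibitors are allogeneic antibodies to FVIII that reduce or eliminate the activity of FVIII proteins in clotting factor concentrates".

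Protocol 18.2.4, as changed by Amendment 6, summarises and lists recovery and trough levels and then adds: "A sensitivity analysis will be performed excluding troughs > 30% and excluding recoveries < 30" per cent. The stated aim is to remove troughs recorded as recoveries, and the reverse, that data cleaning could not resolve. SAP 2.2.4 keeps the summary and listing but not this sensitivity analysis.

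**The concern.** An exclusion that depends on the value of the outcome truncates that outcome. Here the truncation falls at zero on a measure that the protocol follows partly as a sign of inhibitor formation, and inhibitors are described as able to abolish FVIII activity. A post-dose value no higher than the pre-dose value has two very different explanations. One is a procedural error, such as swapped tubes or a dose not given. The other is a dose that produced no measurable rise. The first should be excluded and the second should be seen, but the rule does not tell them apart. Patients with confirmed inhibitors of 0.6 to 5 BU/mL may remain on treatment under Amendment 18 (protocol 8.3.2.2), so their samples can be in the data.

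At stake is the completeness of the steady-state recovery summary and of the display meant to show whether recovery differs by anti-PEG status.

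**Working it through.** The plan gives no figure for this rule, so there is none to reproduce.

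**1. What the rule removes.** With IR = (C30min − C0) / dose and dose > 0, C30min ≤ C0 holds exactly when IR ≤ 0. The rule is a cut at zero on recovery itself.

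**2. Which pairs meet it.** Inputs from the documents: a rise of about 2% (0.02 U/mL) per U/kg (protocol 5.3.2, Amendment 2) and doses of 50 and 75 U/kg (protocol 5.3.1). Expected rises are 50 × 0.02 = 1.00 U/mL and 75 × 0.02 = 1.50 U/mL. Assumed inputs: true trough of 0.01, 0.03, 0.05 or 0.10 U/mL and independent log-normal assay error with a CV of 10% or 20%. For each of these 16 settings, 400,000 pairs were simulated with true post-dose activity = trough + f × 0.02 × dose, where f is the fraction of normal recovery retained.

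| f | Pairs removed, range over 16 settings |
|---|---|
| 100%, 60%, 30% | 0% |
| 10% | 0 to 0.7% |
| 5% | 0 to 7.6% |
| 2% | 0 to 26.0% |
| 1% | 0 to 36.9% |
| 0 | about 50% |

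A swapped pair with normal recovery is the mirror image of the first row and is essentially always removed. At true zero with measurable activity, about half the pairs go, according to the sign of the assay error. If both values were below quantification and both set to LLOQ/2 they would tie and always be removed, but the SAP states that substitution only for the pre-dose level model.

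**3. Effect on a mean.** Let k zero recoveries be removed from n values, the others being 0.020. The all-data mean is 0.020 × (n − k)/n, the reported mean is 0.020, and the overstatement is n/(n − k) − 1. The value n = 105 is the planned number of prophylaxis completers; k is assumed.

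- k = 1: all-data mean 0.0198; 105/104 − 1 = 1.0%
- k = 2: all-data mean 0.0196; 105/103 − 1 = 1.9%
- k = 3: all-data mean 0.0194; 105/102 − 1 = 2.9%

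For scale only, in an assumed antibody-positive group of 20, removing 1, 2 or 5 zeros gives 5.3%, 11.1% or 33.3%. No mean by antibody status is planned. In the planned plots the effect is 1, 2 or 5 missing points.

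**4. Whether another analysis restores the values.**

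- The all-observed-data analysis in SAP 2.2.4.1 stands under Single dose PK.
- The all-data sensitivity analysis under Steady state PK belongs to the pre-dose level model, using main phase plus extension part 1 data and data up to Visit 8.
- Neither covers steady-state incremental recovery or the anti-PEG plots.
- The PK changes listed in SAP section 3 do not include the rule.

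**The case against.** The rule has a sensible purpose. With an expected rise of about 1 U/mL, a non-positive difference may well be a swapped tube or a dose not given, and protocol 18.2.4 shows that swaps were anticipated. The recovery thresholds the protocol acts on are partial losses: below 60% of the screening value (8.3.2.1) and 66% of expected (8.3.2.2). The simulation confirms that such values are kept. The rule also appears to be carried over from earlier reporting, so changing it could make accumulated results differ from the interim reports. All of this stands and limits the point, but none of it supplies a reason to exclude a pair with no documented error.

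Four stronger readings are tempting, and the documents do not support them.

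- *The rule could hide inhibitors.* Inhibitors are detected by central Bethesda tests at scheduled visits and confirmed on a second sample. A single positive test is a MESI, and inhibitory antibody formation is always an SAE. The recall for low recovery with binding antibodies (8.3.2.1) operates during conduct, outside the SAP exclusions.
- *The rule deletes zero recoveries caused by anti-PEG antibodies.* The documents never say that these antibodies abolish recovery; they only plan plots by status.
- *The protocol had a screen that spared true loss.* Protocol 18.2.4 gives two separate cut-offs, not a paired condition. A recovery below 30% would be dropped even if the trough were also low, so that screen would remove a true zero too. The contrast is only that the protocol confined its exclusions to a sensitivity analysis.
- *The values vanish from the report.* SAP 2.2.4 lists recovery and trough levels; whether excluded values appear there or are flagged is not stated.

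**Conclusion.** The point holds in limited form. The main steady-state analysis contains an outcome-dependent exclusion that removes incremental recoveries at or below zero, whatever their cause and whatever the antibody status. These filtered values feed the part 2 recovery summary and the anti-PEG plots, with no all-data counterpart. The identity between the rule and a cut at zero is exact. The finding that the rule acts almost only on complete loss or procedural error rests on the assumed troughs and assay CVs and on the protocol's 2% per U/kg.

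The effect on the overall mean is small for a handful of cases: 1.0% to 2.9% for one to three zeros in 105. The main consequence is that an individual with complete loss could be absent from a display meant to reveal it. How many pairs are affected, if any, cannot be told from the documents. The co-primary inhibitor rate and the detection of inhibitors do not depend on this rule.

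**What to change.** - In the main steady-state recovery analysis, replace the rule with exclusion of pairs that have a documented sample swap or a documented dosing or sampling error.
- Repeat the incremental recovery summary and the anti-PEG plots on all data.
- List every excluded pair with the reason and the patient's inhibitor, N8-GP-binding and anti-PEG status.
- Record the rule in SAP section 3 as a change from protocol 18.2.4, where value-based exclusions were confined to a sensitivity analysis.

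The cost is a little more data review before lock, one repeated set of outputs, and a note explaining any difference from the earlier interim reports.

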5.3.1 Prophylaxis

Main Phase: In the prophylaxis arm, one single bolus dose of 50 U/kg BW of N8-GP is administered intravenously every 4 days (96 hours interval). The dose chosen is based on phase 1 data from the pathfinder™ 1 trial and is chosen to ensure a trough level of >1% FVIII:C activity in the majority of patients in the prophylaxis arm. During treatment a shortening of the dosing interval for prophylaxis to twice weekly may be undertaken at the Investigator's discretion, if deemed necessary for the individual patient (see section 5.3.2). If the dosing regimen is changed to twice weekly, doses should be separated with at least 3 calendar days and no more than 4 calendar days. Other changes of the dose or dosing interval for prophylaxis are not allowed within the trial. However, extra doses of N8-GP will be administered if a patient experiences a treatment requiring bleeding episode or in case of minor surgery.

Extension Phase part 1: *The prophylaxis dose of N8-GP is administered in the non-randomised group every 4 days or in the randomised group every 4 day or every 7 day depending on which treatment arm the patient is allocated to. Based on the bleeding pattern, the Investigator may*

change the every 7 day prophylaxis treatment to an every 4 day treatment regimen (the non-randomised arm), but changing vice versa is not permitted. The recommended doses to treat a bleeding episode will be the same as in the Main Phase. Patients moving from the randomised prophylaxis treatment every 7 day to the non-randomised prophylaxis treatment every 4 day will not be replaced in the randomisation distribution. The twice weekly regimen will only be allowed in the Extension Phase for patients who already in the Main Phase changed to twice weekly.

Extension Phase part 2: *During this period it is possible to adjust the prophylaxis treatment of patients to an individualised regimen. Treatment regimens ranging from once weekly to every 4 day will be allowed: every 4 day, every 5 day, every 6 day or every 7 day. For deciding to change a regimen it is strongly recommended to follow below guidelines for change of regimen:*

- *0-2 bleeding episodes within last 6 months on same regimen would allow a less frequent dosing interval to a lowest frequency of every 7 day*
- *3 or more bleeding episodes within last 6 months on same regimen allows to stay on regimen or change to a more frequent regimen to a highest frequency of every 4 day*

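### The steady-state pre-dose FVIII model keeps samples up to 2 days off schedule and has no term for time since last dose, so mistimed samples enter the estimate uncorrected

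*SAP*

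**What the plan says.** SAP 2.2.4.1, under Steady state PK, lists the exclusions for pre-dose activity, post-dose activity and incremental recovery. The rule that concerns timing removes "Samples drawn more than ± 2 days from planned time", together with samples taken within two prophylaxis intervals of the last bleed treatment. It does not say whether planned time means hours since the last dose or the scheduled visit date.

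The remaining pre-dose values, taken after at least four prophylaxis intervals, go into a mixed model on the log scale "with dose and age as a factor and patient as a random effect". Values below the lower limit of quantification (LLOQ) are replaced by half that limit. The analysis is run on main phase and extension part 1 data, again on data up to Visit 8, and again for the randomised part 1 patients. The companion analysis is described thus: "A sensitivity analysis including all data after at least 4 PPX dosing intervals will also be performed for both cases".

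SAP Table 2-2 defines trough as the activity just before the next dose. For C30min it warns that "The value is sensitive to deviations from the scheduled sampling time". It gives no such warning for trough. For single-dose PK, the SAP does commit to using actual time points.

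**The concern.** FVIII activity falls exponentially between doses, so a pre-dose level can be interpreted only together with the hours since the last dose. The model leaves that variable out while the exclusion rule tolerates a wide spread of it. Neither alternative analysis tightens the timing: one puts the off-window samples back, and the other only truncates follow-up at Visit 8.

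Recovery and trough levels in prophylaxis patients are a listed supportive efficacy endpoint (Protocol 4.2.2.2), and trough is also a PK endpoint. Protocol 5.3.1 justifies the every-4-day dose by a trough above 1% in most patients. If late samples pull the estimate down, the reported pre-dose level partly reflects attendance and not only the regimen.

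**Working it through.** The documents give no expected value, spread or sample size for this estimate, so there is no stated figure to reproduce. The check asks what the rule admits and how far a mistimed sample can differ from an on-time one.

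**Window, reading planned time as time since last dose**

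- Every 4 days (96 h): 96 ± 48 gives 48 to 144 h. Protocol 6.4 reschedules visits with less than 96 h of wash-out before inhibitor and antibody testing, so the realistic range is 96 to 144 h.
- Every 7 days (168 h): 168 ± 48 gives 120 to 216 h. The 96 h minimum removes none of it.

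**Half-life (assumed, because only a 1.6-fold prolongation is stated)**

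- Lower bound. Protocol 5.3.2, as amended, takes a rise of about 2% per unit, so 50 U/kg gives 50 × 2% = 100%. A level above 1% at 96 h (Protocol 5.3.1) needs a half-life above 96 × ln 2 / ln 100 = 14.4 h.
- Upper bound. SAP 2.2.4.1 reads pre-dose activity above 5% as possible inadequate wash-out. The second PK session follows a 7-day wash-out (Protocol 6.4). Falling from 100% to 5% in 168 h gives 168 × ln 2 / ln 20 = 38.9 h.

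**Effect on one sample**, assuming first-order decline: ratio to the on-time level = 2^(−delay / half-life).

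| Half-life (h) | 24 h late | 48 h late |
|---|---|---|
| 14.4 | 0.31 | 0.10 |
| 18 | 0.40 | 0.16 |
| 24 | 0.50 | 0.25 |
| 38.9 | 0.65 | 0.43 |

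For every-7-day dosing, a sample 48 h early reads high by the inverse factor, 2.35- to 10.1-fold.

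**Levels at an assumed 18 h**, using 2% × dose × 2^(−h / half-life) / (1 − 2^(−interval / half-life)):

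- Every 4 days, 50 U/kg: 2.5% at 96 h and 0.4% at 144 h. A 48 h delay crosses the 1% level that the dose was chosen to exceed.
- Every 7 days, 75 U/kg: 1.5% at 120 h, 0.23% at 168 h and 0.04% at 216 h. The half-LLOQ substitution may raise the lowest values; the LLOQ itself is not given.

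**Effect on the geometric mean.** On the log scale the shift depends on the average delay.

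- 10% of samples one day late: average delay 2.4 h, factor 2^(−2.4/18) = 0.91 at 18 h and 2^(−2.4/24) = 0.93 at 24 h.
- Bounding case, all samples spread evenly over 0 to 48 h late: average delay 24 h, factor 0.40 at 18 h and 0.50 at 24 h.

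**The case against.** The strongest reply is that little depends on this estimate. The SAP's stated scope is extension part 2, and it says that data to the end of part 1 had already been analysed and reported. In part 2 only incremental recovery is summarised by visit. This limits materiality. The SAP nevertheless still specifies the model as its estimate of the steady-state pre-dose level.

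A second reply is that a sample drawn just before a late dose still meets the Table 2-2 definition of trough. That is literally so, but such a value describes the interval the patient happened to leave and not the regimen's nominal interval.

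Third, the protocol restricts both sides under every-4-day dosing: the 96 h minimum wash-out, and Protocol 8.5, under which prophylaxis doses should be no more than 96 h apart. The edges of the window are then departures rather than expected data. This stands as a limit on frequency, although the SAP makes neither rule a data exclusion.

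Fourth, half-LLOQ substitution would flatten a fitted time slope, so a covariate alone is not a complete remedy. This is correct, and the fix allows for it.

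A reader might also infer three stronger things that the documents do not support.

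- That every-4-day samples at 48 h routinely inflate the trough. The wash-out rule should largely remove them.
- That errors reach 16-fold. This needs a 12 h half-life, which puts the 96 h level at 0.39%, against the plan's target of more than 1%.
- That a comparison of the randomised regimens is invalidated. SAP 2.10 plans a between-regimen ratio for bleeding rate only; pre-dose levels are summarised by regimen without a formal comparison.

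**Conclusion.** The point holds as a minor one. The timing window is wide, planned time is undefined, and the model has no term for time since dose, so off-schedule samples enter the pre-dose estimate uncorrected. The expected bias is downward for every-4-day dosing and can go either way for every-7-day dosing.

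Individual late samples can read several-fold low (0.10 to 0.43 at 48 h). These figures rest on first-order decline and on the assumed half-life bracket of 14.4 to 38.9 h. The effect on the mean cannot be fixed from the documents, because they contain no sampling-time distribution: it is modest if few samples are late and about half or more if most are. It would therefore go too far to say that the reported estimate is driven by lateness rather than by the regimen.

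If planned time means the visit date, time since dose is controlled even less. The endpoint is supportive, the model covers main phase and extension part 1 data, and no primary conclusion depends on it.

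**What to change.** 1. Define planned time as time since last dose.
2. Add actual hours since last dose to the mixed model, linear on the log scale with a regimen-specific slope, and report the estimate at the nominal 96 h or 168 h.
3. Treat values below the LLOQ as left-censored, or at least show how sensitive the result is to the half-LLOQ rule, so that the slope is not flattened.
4. Keep the current model as a sensitivity analysis, and report the distribution of sampling times by regimen.

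The cost is slightly more analysis work. No new data are needed: last-dose date and time are checked at visits (Protocol 8.1.2.1 and 8.1.4), dose times are in the eDiary (8.4.3), and exact sampling times must be documented (8.3.7.3). Because part 1 results have been reported, the adjusted estimate would stand beside them as a supplement.
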